# 8.2 Exclusion Criteria

Subjects will not be eligible to participate in this study if any of the following exclusion criteria are met:

- 1. Individuals meeting DSM-V substance use disorder criteria for alcohol, benzodiazepines, central nervous system (CNS) stimulants, or other drugs of abuse (excluding caffeine, tobacco or tetrahydrocannabinol [THC]/marijuana).
- Any clinically significant abnormality on the basis of medical history, vital signs, physical examination, 12-lead electrocardiogram (ECG; Fridericia's corrected QT interval [QTcF] ≥450 msec. for males or ≥470 msec. for females), and laboratory evaluations (including hematology, clinical chemistry, urinalysis at Screening), in the opinion of the Investigator.
- 3. Significant symptoms, medical conditions, or other circumstances which, in the opinion of the Investigator, would preclude compliance with the protocol, adequate cooperation in the study or obtaining informed consent, or may prevent the subject from safely participating in study, including subjects who are at a risk for gastrointestinal obstruction or paralytic ileus or who have severe respiratory insufficiency, respiratory depression, airway obstruction,

Clinical Study Protocol HS-15-549

gastrointestinal motility disorders, biliary tract disease, severe hepatic insufficiency, planned surgery and prior treatment with monoamine oxidase inhibitors.

- 4. Use (therapeutic or non-therapeutic) of opioids other than SL BPN.
- 5. Aspartate aminotransferase (AST) levels > 3 X the upper limit of normal, alanine aminotransferase (ALT), levels > 3 X the upper limit of normal, total bilirubin > 1.5 X the upper limit of normal, or creatinine > 1.5 X upper limit of normal on the Screening laboratory assessments, or other clinically significant laboratory abnormalities, which in the opinion of the Investigator may prevent the subject from safely participating in study.
- 6. Pregnant or lactating or planning to become pregnant during the study.
- 7. Diagnosis of, or currently under investigation for, fibromyalgia, complex regional pain syndrome, neurogenic claudication due to spinal stenosis, spinal cord compression, acute nerve root compression, severe or progressive lower extremity weakness or numbness.
- 8. History of chemotherapy or confirmed malignancy (except basal cell or squamous carcinoma of the skin) within the past 2 years.
- 9. Clinically significant history of, or current evidence for, suicidal ideation or those who are actively suicidal, as based on the Columbia-Suicide Severity Rating Scale (C-SSRS; grade 4 or 5).
- 10. Clinically significant history of major depressive disorder that is poorly controlled with medication.
- 11. Hypersensitivity or allergy to BPN or other opioids, or excipients of CAM2038.
- 12. Exposure to any investigational drug within the 4 weeks prior to Screening.
- 13. Participants with a clinically significant history of risk factors of Torsades de Pointes and any existing ventricular tachyarrhythmias such as bigeminy, trigeminy, heart failure, hypokalemia, family history of Long QT Syndrome.
- 14. On medications that have the potential for prolonging the QT interval or who may require such medications during the course of the study along with clinically significant abnormalities on screening electrocardiogram (ECG) readings as deemed by the investigator (Appendix 17.1).
- 15. Requires current use of agents that are strong inhibitors or inducers of cytochrome P450 3A4 (CYP3A4) such as some azole antifungals (e.g., ketoconazole), macrolide antibiotics (e.g., clarithromycin), or protease inhibitors (e.g., ritonavir, indinavir, and saquinavir).
- 16. Intolerance to venipuncture and/or difficulty with venous access, as per the judgment of the Investigator/research staff.
- 17. Is an employee of the Investigator or the study site, with direct involvement in the proposed study or other studies under the direction of the Investigator or study site, or is a family member of an employee or of the Investigator.
- 18. Any pending legal action that could prohibit participation or compliance in the study.

## 8.3 Removal of Subjects from Therapy or Assessment

A subject is free to withdraw his/her consent and discontinue participation in the study at any time for any reason. A subject's participation must therefore be terminated immediately upon his/her request, and the reason(s) for discontinuation appropriately documented.

A subject must be discontinued from the study for any of the following reasons:

- Safety reasons, including AEs or significant concomitant illness, injury, or urgent surgeries/procedures that would, in the judgment of the Investigator, affect assessments of clinical status to a significant extent, require discontinuation of study drug, or both
- Clinically significant QTc interval prolongation following administration of CAM2038 q1w or q4w, as judged by the Investigator and agreed upon by the Medical Monitor
- At the request of the Sponsor, regulatory agency, or Institutional Review Board (IRB)
- Subject is lost to follow-up
- Death of subject

A subject may also be discontinued from the study, at the discretion of the Investigator and/or Sponsor, for any of the following reasons:

- Lack of efficacy
- Subject refuses or is unable to adhere to the study protocol
- Major protocol violation
- Pregnancy
- Use of unacceptable concomitant medication(s) (Section 9.5)

The Investigator must maintain a record of all subjects who discontinue from the study prior to completion; the reason(s) for study discontinuation will be documented. In the event that a subject chooses to withdraw from the study, the Investigator should make a reasonable attempt to obtain and record the reason(s) for withdrawal, if possible, although the subject is not obligated to provide such a reason. In the event a subject is lost to follow-up, a third party could be hired to locate the subject.

All efforts should be made by the Investigator to continue collection of concomitant medications, and AEs in subjects that discontinue study drugs, unless the subject withdraws his/her consent at the time of early discontinuation. Subjects discontinued due to clinically significant QTc interval prolongation should be monitored closely by undergoing daily ECGs, until ECG readings return to baseline, or QTc interval values are no longer judged to be clinically significant. The Investigator should also ask the subject to complete the Follow-up phone-call, provided that the subject has not withdrawn consent. If a subject refuses to complete EOT procedures and/or Follow-up, this information will be recorded.

## 8.4 Study restrictions

In addition to the criteria described in Sections 8.1 and 8.2, the subject must agree to abide by the following study restrictions.

## 8.4.1 Contraception Requirements

Male and female subjects of childbearing potential must be using and willing to continue using medically acceptable contraception during the study. Examples of medically acceptable forms of contraception include:

- True abstinence, defined as sexual inactivity consistent with the preferred and usual lifestyle of the subject. Note: Periodic abstinence (e.g., calendar, ovulation, symptothermal, post-ovulation methods) and withdrawal are not acceptable methods of contraception.
- Hormonal contraceptives (combined oral pill, patch or vaginal ring, intrauterine device or system, progestin implant or injection)
- Surgical sterilization (e.g. vasectomy or bilateral tubal ligation)
- Condom plus spermicidal agent (foam/gel/film/cream/suppository) during sexual intercourse with a female partner. In addition, the female partner should also be on another form of contraception (e.g., occlusive cap/diaphragm/intrauterine device/hormonal contraception, etc.) if she is of childbearing potential.
- To prevent exposure of any partner to the semen from a male subject who has been exposed to the investigational product, male subjects must use a condom during non-vaginal intercourse with any partner male or female.

The chosen contraception method(s) must be followed from the first administration of CAM2038 until at least 3 months after receiving the last dose of the investigational product.

Female subjects of non-childbearing potential are not required to use contraception or undergo pregnancy tests; however, they must be surgically sterile (hysterectomy and/or bilateral oophorectomy/salpingo-oophorectomy, as determined by subject medical history) or congenitally sterile, or must be post-menopausal. Post-menopausal is defined as being amenorrheic for at least 2 years without another cause or amenorrheic for at least 1 year without another cause and a documented follicle stimulating hormone (FSH) level ≥50 mIU/mL. If females are not amenorrheic for 2 years or amenorrheic for 1 year with a documented FSH level ≥50 mIU/mL or surgically sterile, then females will have to undergo the pregnancy procedures as stated in Table 1 (Group 1), Table 2 (Group 2), and Table 3 (Group 3).

Female subjects must not donate ova starting at Screening and throughout the clinical study period and for 3 months after final investigational product administration.

Male subjects must not have unprotected sexual intercourse with a female who is pregnant or breastfeeding during the study and for 3 months after final investigational product administration.

Subjects must not donate sperm throughout the study and for at least 3 months after receiving the last dose of the investigational product.

## 8.4.2 Dietary and Fluid Restrictions

Subjects will be required to fast from all food or drink (except water) for at least 4 hours before the Screening visit and the EOT visit. During the in-house stay in the CRU, standardized meals and fluids will be provided.

No food and drink containing grapefruit, Chinese grapefruit (pomelo), or Seville orange (including marmalade) will be allowed from 48 hours before each visit to the CRU and while subjects are confined to the CRU.

Quinine-containing products (e.g., tonic water) will not be allowed from 7 days before each confinement to the CRU and while subjects are confined to the CRU.

To avoid falsifying urine drug screen (UDS) results, no food or drink containing poppy seeds (e.g., specialty breads and muffins) will be allowed from 72 hours before Screening and 7 days before the first administration of CAM2038 through the end of the study.

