#### GROUP 3:

Each subject in Group 3 will participate in the study for up to 21 weeks, including up to approximately 3 weeks for screening, 17 weeks for treatment, and approximately 1 week for follow-up. Single daily doses of 24 mg SL BPN will be administered in the mornings on Day 1 through Day 7 for a total of 7 doses. This will be followed by SC injections of 160 mg CAM2038 q4w in the buttock, rotating between right and left buttock and injection site per Appendix 17.2, on Day 8, Day 36, Day 64 and Day 92, for a total of 4 doses. Following the first CAM2038 q4w administration, subjects will attend an interim visit on Day 9 to evaluate safety and tolerability of the transition from SL BPN to CAM2038 q4w.

Following administration of the first 3 doses of CAM2038 q4w, PK samples will be collected pre-dose and at scheduled times post-dose on an outpatient basis to determine achievement of steady state. To characterize steady state PK of BPN and norBPN and evaluate relative bioavailability CAM2038 q4w as compared with SL BPN, subjects will be confined to the CRU and serial PK samples will be collected for up to 24 hours following the seventh dose of SL BPN administered on Day 7, and following the fourth dose of CAM2038 q4w administered on Day 92. Subsequent PK samples will be collected up to 28 days post-dose on an outpatient basis.

At each study visit, safety and efficacy assessments will be conducted at pre-specified times. Subjects will also be required to record their worst daily pain and average daily pain using an 11-point NRS on an electronic device.

For all Groups, subjects will be transitioned to standard care as needed at the EOT or EOT-OLE visit, as applicable, and a follow-up call will be conducted approximately 7 days after the last study visit. Subjects who discontinue early will undergo EOT visit assessments, including PK sampling and urine toxicology.

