## 8.4.4 Activity and Exercise

Subjects should refrain from carrying out heavy physical training (e.g., long distance running, weight lifting, or any physical activity to which the subject is not accustomed) from 7 days before the first administration of CAM2038, while subjects are confined to the CRU, and through the EOT visit. Subjects should neither start any new physical training nor increase the intensity of their usual training during study participation. Subjects may participate in light recreational activities during confinement to the CRU (e.g., watch television, play computer games, read).

Subjects should refrain from driving a car or other vehicles, operating machines or engaging in potentially dangerous activities that require focused attention and intact physical balance until the subjects understand how CAM2038 affects their focus.

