#### Table 2: Schedule of Assessments – Group 2 (128 mg CAM2038 q4w) Page 2 (128 mg CAM2038 q4w)

a Subjects must voluntarily provide written informed consent prior to any study-related procedures being performed.

b Prior to treatment on Day 1, all Inclusion and none of the Exclusion criteria must be met.

c Vital signs (temperature, blood pressure, pulse rate, respiratory rate) will be measured pre-dose and 15 minutes post-dose after each CAM2038 q4w administration. Vital signs will also be measured at the Screening, Day 2 and EOT visits, and at each admission.

d ECG will be measured at the Screening and EOT visits, and pre-dose and 6 (±1) hours after each CAM2038 q4w administration. After dose 4, ECGs will be measured at 1, 4, 6, 10, 24, 72, 120, 168 (7 days), 336 (14 days) and 672 (28 days) hours post-dose.

e Assessment of serum sodium, bicarbonate, potassium, magnesium, calcium levels only.

f A serum pregnancy test will be performed at Screening and EOT visits. An "in-office" urine pregnancy test will be required prior to all doses of CAM2038 q4w (for women of childbearing potential) during days 1 through 113. An "in-office" urine pregnancy test will be required prior to all doses of CAM2038 q1w (for women of childbearing potential) for those women that continue to the extension phase.

Clinical Study Protocol Braeburn Pharmaceuticals HS-15-549 g Any spontaneously reported AEs will be recorded after the subject signs the ICF. In addition, AEs will be elicited using a non-leading question each time the subject visits the clinic and once daily during inpatient stays.

Study Period/Phase:	Screening	Treatment Phase											Open-label Safety Extension Phase							
Treatment:					12	28 mg	CAN	A2038	8 q4w				CAM2038 q1w							
CAM2038 q4w Dose:		1	Dose	1	Do	se 2	Do	se 3		D	ose 4									
Day:	-21 to -1	D1	D2	D8 D15 D22	D29	D31 D36 D43 D50	D57	D59 D64 D71 D78	D85	D86	D87, D88 D89, D90 D92, D95 D99, D106	D113/ EOT	D120	D127	D134	D141	D148	D155/ EOT	D162	
C-SSRS h	X	X	Х		Х		X		X			Х			X			X		
Injection Site Examination 		X	Х	X	X	X	X	Х	X	X	Х	Х	X	Х	X	X	X	X		
PK samples		Xj		хj	Xk	X k	X k	X k	X l	X	X m	Х						X		
cows n		X	Х		Х		X		X			Х						X		
sows n		X	Х		Х		X		X			Х						X		
UDS and breath alcohol test	X	X	Х	X	Х	Х	X	Х	X	Х	Х	Х			X			X		
NRS for Pain 	X	X	Х	X	Х	Х	X	Х	X	Х	X	Х	X	X	X	X	X	X		

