**Clinical Study Protocol** 

#### HS-15-549

#### **Braeburn Pharmaceuticals**

CONFIDENTIAL

Study Period/Phase:	Screening	Treatment Phase													
Treatment:		GI	DDN						160	mg CAM20	38 q4w				FU
		SL	BPN		D	ose 1	]	Dose 2	]	Dose 3			Dose 4		
Day:	-21 to -1	D1- D6	D7	D8	D9	D15 D22 D29	D36	D38, D43, D50, D57	D64	D66, D71, D78, D85	D92	D93	D94, D95, D96, D97, D99, D102, D106, D113	D120/ EOT	D127
Concomitant Medications/Procedures	Х	Х	Х	X	Х	Х	Х	Х	Х	Х	Х	Х	Х	Х	Х
C-SSRS i	Х	Х	Х	X	Х		X		X		Х			Х	
Injection Site Examination j				X	Х	Х	X	Х	Х	X	Х	Х	Х	Х	
PK samples			X k	Xk		X k	Xl	xl	x l	Xl	X m	X m	X m	X m	
COWS n		X	Х	X		Х	X	X	Х	X	X		X	Х	
sows n		Х	Х	X		Х	Х	X	Х	X	X		Х	Х	
UDS and breath alcohol test	Х	Х	Х	X	Х	Х	Х	X	Х	X	Х	Х	X	Х	
NRS for Pain o	Х	Х	Х	X	Х	Х	X	X	X	X	Х	Х	X	Х	
SL BPN administration		Х	Х												
CAM2038 q4w SC injection p				X			X		Х		X				
Admission to CRU			Х								X				
Discharge from CRU				Xq								Х			
Outpatient visits		Х			Х	Х	X	X	Х	X			X	Х	
Telephone call															X
Transfer to previous BPN therapy														Х	

C-SSRS-Screening will be performed at Screening and then C-SSRS-since last visit will be performed at other subsequent visits.

J Injection site examinations will occur at each visit after CAM2038 q4w administration and once daily during inpatient stays.

k Pharmacokinetic samples will be collected at pre-dose (within 45 minutes), 10, 20, 30 and 40 minutes, and 1, 1.5, 2, 3, 4, 6, 10 and 24 hours after SL BPN dose 7, and pre-dose, 168 hrs (7 days), 336 hrs (14 days) and 504 hrs (21 days) after CAM2038 q4w dose 1. If a subject terminates early from the study, then a PK blood sample is to be drawn.

 Pharmacokinetic samples will be collected at pre-dose, one sample any time between 4 and 8 hrs post-dose, approximately 48 hrs, 168 hrs (7 days), 336 hrs (14 days) and 504 hrs (21 days) after CAM2038 q4w doses 2 and 3.

m Pharmacokinetic samples will be collected at pre-dose, 0.5, 1, 2, 4, 6, 10, 24, 48, 72, 96, 120, 168 (7 days), 240 (10 days), 336 (14 days), 504 (21 days) and 672 (28 days) hours after CAM2038 q4w dose 4.

n COWS and SOWS will be performed pre-dose on all dosing days and at each other visit.

 Average daily NRS pain score will be recorded using an electronic device each day.

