Promethazine	Phenergan®	Antipsychotic / Antiemetic
Propofol	Diprivan ® , Propoven ®	Anesthetic, general
Quetiapine	Seroquel®	Antipsychotic, atypical
Quinidina	Quinaglute ® , Duraquin ® , Quinact ® , Quinidex ® ,	Antiorrhythmic
Quimaine	Cm-Quine, Quinorae	Antiarrhythmic
Quinine sulfate		Antimalarial
Ranolazine	Ranexa®, Ranozex®	Antianginal
Rilpivirine	Edurant ® , Complera ® , Eviplera ®	Antiviral
Risperidone	Risperdal®	Antipsychotic, atypical
Ritonavir	Norvir®	Antiviral
Saquinavir	Invirase®(combo)	Antiviral
Sertraline	Zoloft®, Lustral®, Daxid®, Altruline®, Besitran®, Deprax®, Elrval®, Emergen®, Gladem®, Implicane®, Sedoran®, Sealdin®, SerivoLowfin®, Stimuloton®, Tresleen®, Sertralin Bluefish®	Antidepressant, SSRI
Sevoflurane	Ulane®, Sojourn®	Anesthetic, general
Solifenacin	VESIcare®	Muscle relaxant
Sorafenib	Nexavar®	Tyrosine kinase inhibitor
Sotalol	Betapace ® , Sotalex ® , Sotacor ®	Antiarrhythmic
Sunitinib	Sutent®	Kinase inhibitor
Tacrolimus	Prograf®, Prograf®, Advagraf®, Protopic®	Immunosuppressant
Tamoxifen	Nolvadex®(discontinued 6/13), Istubal®, Valodex®	Anticancer
Telaprevir	Incivek ® , Incivo ®	Antiviral
Telavancin	Vibativ®	Antibiotic
Telithromycin	Ketek®	Antibiotic

Version: 5.0, 05 OCT 2016

Page 75 of 87

Clinical Study Protocol HS-15-549		Braeburn Pharmaceuticals CONFIDENTIAL
Generic Name	Brand Names (Partial List)	Drug Class
Tetrabenazine (Orphan		Monoamine Transporter
drug in US)	Nitoman®, Xenazine®	Inhibitor
Thioridazine	Mellaril®, Novoridazine®, Thioril®	Antipsychotic
Tizanidine	Zanaflex ® , Sirdalud ®	Muscle relaxant
Tolterodine	Detrol®, Detrusitol®	Muscle relaxant
Toremifene	Fareston®	Estrogen agonist/antagonist
Torsemide	Demadex ® , Diuver ® , Examide ®	Diuretic
	Desyrel® (discontinued 6/13), Oleptro®, Beneficat®, Deprax®, Desirel®, Molipaxin®, Thombran®,	
Trazodone	Trazorel®, Trialodine®, Trittico®, Mesyrel®	Antidepressant, SARI
Trimipramine	Surmontil®, Rhotrimine®, Stangyl®	Antidepressant, Tricyclic
Vandetanib	Caprelsa®	Anticancer
Vardenafil	Levitra®	Phosphodiesterase 5 inhibitor
Vemurafenib	Zelboraf®	Kinase inhibitor
Venlafaxine	Effexor®, Efexor®	Antidepressant, SNRI
Voriconazole	VFend®	Antifungal
Vorinostat	Zolinza®	Histone deacetylase inhibitor
Ziprasidone	Geodon®, Zeldox®	Antipsychotic, atypical

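### The poppy-seed and heavy-training bans run from the first CAM2038 dose, so Group 3 has no lead-in before Day 1; separately, the quinine window does not match the ECG schedule

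*Protocol*

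**What the plan says.** **Poppy seeds.** Protocol Section 8.4.2 gives the purpose of this ban as keeping urine drug screens from being falsified. It applies "from 72 hours before Screening and 7 days before the first administration of CAM2038 through the end of the study".

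**Heavy training.** Section 8.4.4 uses the same anchor: "from 7 days before the first administration of CAM2038, while subjects are confined to the CRU, and through the EOT visit". A further sentence there, not tied to any dose, tells subjects not to start new training or train harder while in the study.

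**Quinine.** Section 8.4.2 has a different anchor: "Quinine-containing products (e.g., tonic water) will not be allowed from 7 days before each confinement to the CRU", and during confinement. It states no reason. Appendix 17.1 lists "Quinine sulfate" among drugs that may prolong QTc.

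**Schedule.** In Groups 1 and 2 the first CAM2038 injection is on Day 1. Group 3 takes sublingual buprenorphine on Days 1 to 7, and its injections come "on Day 8, Day 36, Day 64 and Day 92, for a total of 4 doses" (Section 7.1). In Table 3 the row "UDS and breath alcohol test" is marked under the Day 1 to Day 6 column, under Day 7 and at each later visit.

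**The concern.** Group 3 was added in Amendment 4, and in this group alone Day 1 is not the day of the first CAM2038 dose. Sections 7.1, 9.1 and 10.2 still contain sentences that treat the two as the same day. A restriction counted back from the first CAM2038 dose therefore starts a week later, relative to entry, in Group 3 than in Groups 1 and 2.

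At stake is the quality of the earliest Group 3 data. A qualitative opiate screen taken before poppy seeds have been excluded for long enough can be positive because of food. Protocol Section 12.3.4 and SAP Section 9.2 summarise positive results by group and do not set the sublingual-phase screens aside. The Day 1 chemistry panel (Table 3, footnote e) includes creatine phosphokinase, aspartate transferase and lactic dehydrogenase (Table 4), for which avoiding heavy exercise beforehand is a sensible precaution.

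The quinine window raises a separate question. ECGs are scheduled throughout treatment, but the window opens only around confinement. In Groups 1 and 2 it misses Day 1, the randomization date to which SAP Section 6.1 ties baseline.

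**Working it through.** The plan states no figure to reproduce. The check is day arithmetic, taking Day -1 as the day before Day 1 (no Day 0) and the Table 3 mark under Days 1 to 6 as one screen per day.

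**1. Start of the poppy-seed and training bans** (first CAM2038 dose minus 7 days)
- Groups 1 and 2: 7 days before Day 1 = Day -7.
- Group 3: Day 8 - 7 = Day 1.

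**2. Lead-in before each Group 3 screen** = (day - 1) × 24 hours

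| Day | 1 | 2 | 3 | 4 | 5 | 6 | 7 | 8 |
|---|---|---|---|---|---|---|---|---|
| Hours | 0 | 24 | 48 | 72 | 96 | 120 | 144 | 168 |

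Days 1 to 3 fall short of the 72 hours set for Screening. All 7 sublingual-phase days fall short of the 168 hours that Groups 1 and 2 have on Day 1. No day is without a ban.

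**3. Share of the Group 3 urine data.** Post-Screening screens per completer in Table 3: 7 (sublingual) + 5 (dose 1) + 5 (dose 2) + 5 (dose 3) + 11 (dose 4 to EOT) = 33. The three short-lead-in screens are 3/33, about 9%. With 16 subjects, 3 × 16 = 48 of 33 × 16 = 528 samples.

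**4. Quinine windows.** The rule is "will not be allowed from 7 days before each confinement to the CRU and while subjects are confined to the CRU", so each window runs from 7 days before admission to discharge.
- Group 1, confined for 24 hours from Days 22, 29, 36 and 43: Days 15 to 44.
- Group 2, confined on Days 85 to 86: Days 78 to 86.
- Group 3, confined on Days 7 to 8 and 92 to 93: Day -1 to Day 8, and Days 85 to 93.

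**5. Treatment-phase ECGs from footnote d of Tables 1 to 3**, excluding Screening and the extension. In Groups 2 and 3 the core is "pre-dose and 6 (±1) hours after each CAM2038 q4w administration", plus serial tracings after dose 4.
- Group 1: 2 around dose 1 + 9 × 4 after doses 4 to 7 = 38; the Day 50 EOT tracing is the 168-hour one. Outside the window: Days 1, 2, 45, 46, 47 and 50 = **6 of 38**.
- Group 2: 2 × 4 = 8, plus 9 more after dose 4 (10 times, of which 6 hours is already counted) = 17. Outside: two each on Days 1, 29 and 57, and one each on Days 88, 90, 92, 99 and 113 = 6 + 5 = **11 of 17**.
- Group 3: 2 on Day 1 + 17 = 19. Outside: two each on Days 36 and 64, and one each on Days 95, 97, 99, 106 and 120 = 4 + 5 = **9 of 19**. Day 1 is inside, with about 1 day of lead-in.

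Counting the days ticked in the table grids instead gives 7 of 27, 22 of 25 and 11 of 21 outside. All 6 extension ECG visits in each of Groups 1 and 2 are also outside.

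**The case against.** **The sentence may be continuous.** Section 8.4.2 could mean one ban from 72 hours before Screening to the end of the study, which would leave no poppy-seed gap. That reading makes the second start point redundant, so two windows are more natural. The ambiguity itself needs clearing up, and this reading does not help Section 8.4.4, which has a single start point.

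**The sublingual-phase screens are not left uncovered.** A reader might infer that they are. The ban is in force on every one of Days 1 to 7; only the lead-in is missing, and it matters mainly for Days 1 to 3. The 7 days are a lead-in to first dosing, not a standard for each sample.

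**No comparison is planned for the gap to bias.** Because protection differs between phases, a reader might infer a bias in favour of CAM2038 over sublingual treatment. Urine results are exploratory and summarised by group, with no planned contrast between the two phases.

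**Eligibility.** Exclusion 4 concerns use of other opioids, and nothing in the plan makes a positive Day 1 screen disqualifying in itself. An effect on the eligibility recheck would be speculation.

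**Training.** The rule against new or intensified training applies throughout participation and partly covers the Day 1 chemistry.

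**Quinine.** The protocol gives no QTc purpose for this ban, Appendix 17.1 lists a drug rather than tonic water, and exclusion 14 addresses QT-prolonging medications. The counts therefore set the window against a standard the protocol never declares. This stands, and it limits the point to a request for reconciliation.

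**Conclusion.** The point holds as an anchoring error for Group 3, with modest consequences. On the two-window reading, Group 3's poppy-seed ban starts on Day 1, and 3 of its 7 sublingual-phase screens (about 9% of a completer's post-Screening screens) have less than the protocol's own 72-hour lead-in. The heavy-training restriction also loses its 7-day lead-in before the Day 1 chemistry, partly offset by the general training rule.

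The documents give no rate of food-related positives, so the effect cannot be sized. For scale only, one subject in 16 is 1/16 = 6.25 percentage points of incidence.

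On quinine, the mismatch with the ECG schedule is real, but its consequence is not established. A reader might infer that the QTc baseline is compromised in every group, or that a raised baseline would hide later increases. Group 3's Day 1 ECG is inside the window. Most of the ECGs outside it are post-baseline, where any quinine effect would add to the change. The criterion of QTc above 500 msec in Section 10.5.5 does not use baseline. The documents give no effect of dietary quinine on QTc.

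**What to change.** 1. In Sections 8.4.2 and 8.4.4, replace *first administration of CAM2038* with *first administration of study drug (Day 1 in every Group)*. Group 3's bans then start on Day -7, as in Groups 1 and 2, and its Day 1 screen has 168 hours of lead-in. State in 8.4.2 whether the ban also applies between Screening and that date.
2. For Group 3 subjects already enrolled, flag the Day 1 to Day 3 opiate results in the listing as having a short lead-in.
3. Reconcile the quinine window with the ECG schedule in Tables 1 to 3, at least for the Day 1 baseline ECG, and state the purpose of the ban.

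Items 1 and 2 cost a wording change in two sections and the subject instructions, a listing flag, and one extra week of restriction in Group 3, with no new procedures. Item 3 involves a trade-off for the sponsor to weigh: cover through EOT would mean 112 days (16 weeks, Day 1 to Day 113) in Group 2 and 119 days (17 weeks, Day 1 to Day 120 in Table 3) in Group 3, before any lead-in.
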